Naïve to COPD treatment, or at least one dispensing of the following categories of medications either alone or in combination: 1) SABA or SAMA or SABA+SAMA, 2) LAMA or LABA monotherapy, 3) theophylline or mucolytics, in the 12 months before the index date;

➤ Moderate:

At least one dispensing of LAMA + LABA in the 12 months before the index date;

> Severe:

Occurrence of at least one of the following events in the 12 months before the index date:

- Hospitalisation for COPD
- Recorded diagnosis of pneumonia
- Second course of antibiotics for respiratory tract infections
- Second course of systemic corticosteroids for the treatment of COPD exacerbation
- Two diagnoses of COPD exacerbation without hospitalisation

➤ Very severe:

Occurrence of at least one of the following events in the 12 months before the index date unless other time period is specified:

- Dispensed oxygen therapy
- Dispensed nebuliser therapy

NIS Protocol Page 28 of 48 BI Study Number: 1237-0110 c38660249-01

Proprietary confidential information © 2022 Boehringer Ingelheim International GmbH or one or more of its affiliated

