9.7.1 Main analysis

All variables, including patient characteristics, baseline measures, and outcomes, will be analyzed descriptively.

- For all analyses, variables will be reported as follows: Continuous variables (e.g., age) will be presented as means (with standard deviation, SD) and/or medians (with interquartile range, IQR), minimum, maximum.
- Categorical variables (e.g., sex) will be presented as absolute and relative frequencies.

All analyses will be presented for each treatment group (Tio+Olo vs LABA/ICS) overall. We will first describe formation of the study cohort. Propensity score matching will be used to balance the baseline characteristics of patients in the two treatment groups. The covariates used to calculate the propensity score would be specified in the SEAP. All the analyses will be performed on patients after propensity score matching. Patient characteristics at baseline in patients treated with Tio+Olo and patients treated with LABA/ICS will be described separately using standard descriptive statistics after propensity score matching. Absolute standardized differences (ASDs) will be used to compare the characteristics between the two

NIS Protocol Page 30 of 48 BI Study Number: 1237-0110 c38660249-01

Proprietary confidential information © 2022 Boehringer Ingelheim International GmbH or one or more of its affiliated

groups after propensity score matching, in which a >0.1 ASD indicates a meaningful difference.

For the analysis of the primary outcome, individuals will be followed up from the index date until the first moderate or severe COPD exacerbation. The data after the earliest date of the following would be censored: 1) disenrollment; 2) the end of the study period; 3) death; 4) discontinuation of the index drug (except for switching from the index ICS/LABA to a different ICS/LABA); 5) escalation to triple therapies (ICS/LAMA/LABA free or fix dose combination). Cox proportional hazard regression model will be used to compare the time to event between the two treatment groups, while accounting for the potential baseline differences between them. Other known predictors will also be included in the model as covariates. It will provide an estimate of the hazard ratio (HR) of time to the first moderate or severe COPD exacerbation associated with Tio+Olo use relative to LABA/ICS use, along with 95% confidence intervals (CI). The analysis will be on-treatment.

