Naïve to COPD treatment, or at least one dispensing of the following categories of medications either alone or in combination: 1) SABA or SAMA or SABA+SAMA, 2) LAMA or LABA monotherapy, 3) theophylline or mucolytics, in the 12 months before the index date;

- Moderate:  
At least one dispensing of LAMA + LABA in the 12 months before the index date;
- Severe:  
Occurrence of at least one of the following events in the 12 months before the index date:
  - Hospitalization with a primary diagnosis for COPD
  - Hospitalization with a primary diagnosis for pneumonia
  - Second course of antibiotics for respiratory tract infections; a single course of antibiotic treatment involving multiple dispensings is defined as that involving consecutive dispensings of antibiotics with fewer than 7 days between the end of days of supply of one dispensing and the date of the next dispensing
  - Second course of systemic corticosteroids for the treatment of COPD exacerbation; a single course of systemic corticosteroids involving multiple dispensings is defined as that involving consecutive dispensings with fewer than 7 days between the end of days of supply of one dispensing and the date of the next dispensing.
  - Two diagnoses of COPD exacerbation (ICD-10: J44.1; ICD-9: 491.21) without hospitalisation
- Very severe:  
Occurrence of at least one of the following events in the 12 months before the index date unless other time period is specified:
  - Dispensed oxygen therapy
  - Dispensed nebuliser therapy

Diagnosis codes and drug codes are listed in the annex.

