## **10. DATA ANALYSIS**

### **10.1 MAIN ANALYSIS**

All variables, including patient characteristics, baseline measures, and outcomes, will be analyzed descriptively.

- For all analyses, variables will be reported as follows: Continuous variables (e.g., age) will be presented as means (with standard deviation, SD) and/or medians (with interquartile range, IQR), minimum, maximum.

- Categorical variables (e.g., sex) will be presented as absolute and relative frequencies.

All analyses will be presented for each treatment group (Tio+Olo vs LABA/ICS) overall. We will first describe formation of the study cohort. Propensity score (PS) matching will be used to generate two comparable treatment groups. All covariates, except season of index date, will be used to estimate the propensity score with logistic regression. Patients in LABA/ICS group will be individually matched to patients in the Tio/Olo group with 1:1 ratio. A caliper of 0.06 standard deviation of logit (propensity score) will be used to define the range of estimated PS within which to select the comparator. Within that range the LABA/ICS patient with the closest estimated propensity score to the Tio/Olo patient will be selected.

Patient characteristics at baseline in patients treated with Tio+Olo and patients treated with LABA/ICS will be described separately using standard descriptive statistics after propensity score matching. Absolute standardized differences (ASDs) will be used to compare the characteristics between the two groups after propensity score matching, in which a  $>0.1$  ASD indicates a meaningful difference.

All the analyses for primary outcome and secondary outcomes will be performed on patients after propensity score matching. Baseline characteristic table shell are provided in [Table 1](#). The propensity score matching will be carried out once without re-matching.

For the analysis of the primary outcome, individuals will be followed up from the index date until the first moderate or severe COPD exacerbation. The data after the earliest date of the following event would be censored:

- 1) disenrollment
- 2) the end of the study period
- 3) death
- 4) discontinuation of index drug use (a lapse of 45 days without subsequent prescription)
- 5) switching from Tio/Olo to ICS/LABA or from ICS/LABA to Tio/Olo
- 6) escalation to triple therapies (ICS/LAMA/LABA free or fix dose combination)

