## Appendix 4. ICD codes and operational definition of comorbidities

	Comorbidities:	ICD codes	Operational definition
1.	Diabetes	ICD9: 250 ICD10: E10.x-E11.x	Either inpatient diagnosis or more than twice outpatient diagnosis
2.	Cardiovascular disease	ICD9: 250.7, 401-405, 410-414, 425-428, 429.1-429.3, 441, 442, 458 ICD10: E10.5x, E11.5x, I10-I13.x, I15.x, I20.x-I22.x, I24.x, I25.x, I42.x-I44, I45.xx, I46.x-I49.x, I50.xx, I51.5, I51.7, I51.9, I71.xx, I79.0, I72.x, I77.7x, I95.x	Either inpatient diagnosis or more than twice outpatient diagnosis
3.	Cerebrovascular disease	ICD9: 430-438 ICD10: I60.x-I63.x, I65.x, I66.x, G45.x, G46.x, I67.x-I69.x	Either inpatient diagnosis or more than twice outpatient diagnosis
4.	Cancer	ICD9: 140-199, 200-208 ICD10: C00-C26, C30-34, C37-39, C40-41, C43-49, C4A, C50-58, C60-69, C70-79, C7A, C7B, C80-86, C88, C90-96,	Inpatient diagnosis.
5.	Chronic kidney disease	ICD9: 585-587, ICD10: N18-19, N26.1, N26.9	Either inpatient diagnosis or more than twice outpatient diagnosis
6.	Pneumonia	ICD9: 480-486, 487.0 ICD10: J10.0, J11.0, J12-J18,	Inpatient diagnosis
7.	Cirrhosis	ICD9: 571.2, 571.5, 571.6 ICD10: K70.3x, K74.3, K74.4, K74.5, K74.6x	Either inpatient diagnosis or more than twice outpatient diagnosis

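### The SAP narrows the protocol's pneumonia criterion for Severe COPD to hospitalised cases, so outpatient pneumonia history reaches the propensity score only through partial proxies and its balance is never checked

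*SAP*

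**What the plan says.** **Severity scale.** Protocol 9.3.3 lists, among the events in the prior 12 months that make COPD Severe, a "Recorded diagnosis of pneumonia". The matching line in SAP 7.3 reads "Hospitalization with a primary diagnosis for pneumonia". The visible SAP text gives no reason for the change.

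**Pneumonia comorbidity.** Both documents also list pneumonia as a separate baseline comorbidity. The protocol gives it no operational definition. SAP Appendix 4 gives the codes (the ICD-10 set is "J10.0, J11.0, J12-J18") and requires an "inpatient diagnosis". Cancer is also inpatient only. The other five comorbidities use "Either inpatient diagnosis or more than twice outpatient diagnosis".

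**Propensity score.** Protocol 9.7.1 leaves the choice to the SAP: "The covariates used to calculate the propensity score would be specified in the SEAP". SAP 10.1 states: "All covariates, except season of index date, will be used to estimate the propensity score with logistic regression". Both the severity category and the pneumonia comorbidity therefore enter.

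**Balance check.** SAP 10.1 adjusts for any baseline covariate whose absolute standardised difference (ASD) exceeds 0.1 after matching. The Table 1 shell has one pneumonia row, for the comorbidity.

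**Outcome.** Time to first hospitalisation for community-acquired pneumonia is a secondary outcome in both documents.

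**The concern.** Recent pneumonia is a natural confounder for this outcome. The protocol's rationale reports a higher pneumonia risk with ICS/LABA in an earlier trial, so a prescriber aware of a recent episode may choose accordingly, and a past episode may predict another. In the SAP, both places where a pneumonia diagnosis is used require a hospital stay. A pneumonia treated only in clinic is neither matched on directly nor tabulated.

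The change to the severity scale reaches further than the pneumonia outcome. Severity is in the propensity score used for every outcome, including the primary one, and Protocol 9.9 relies on that scale to reduce bias from missing lung function and disease duration. As written, the two documents can place the same patient in different severity categories.

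**Working it through.** The plan states no figure on this point, so there is none to reproduce. The check compares the texts and then gives a scale calculation on assumed inputs.

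**1. Is the severity line really narrower?** In the same list the protocol names hospitalisation for the COPD event but no setting for pneumonia, which suggests it names a setting when it means one. The SAP line requires both a hospital stay and pneumonia as primary diagnosis. It is narrower.

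**2. What happens to one patient?** Take a patient with a short-acting bronchodilator, one outpatient pneumonia, one antibiotic course and no other severity criterion in the prior year.
- Protocol severity: Severe.
- SAP severity: Mild.
- SAP pneumonia comorbidity: no.
- SAP antibiotic history: yes.
- SAP moderate exacerbation: yes only if COPD was also coded at the visit.

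**3. How good are the proxies?**
- Antibiotic history (SAP 7.3, Appendix 5) covers systemic antibacterials for any indication, plus antimycotics and antimycobacterials. It is sensitive but not specific.
- "Second course of antibiotics for respiratory tract infections" makes a patient Severe, but one treated episode does not qualify.
- A moderate exacerbation needs a COPD code at the outpatient visit.
- An emergency visit counts as a severe exacerbation only if COPD is the primary diagnosis.

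Together they capture part of outpatient pneumonia history, and none isolates it.

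**4. How large could the effect be?** The documents give neither the prevalence of outpatient pneumonia nor its association with later hospitalisation. For a binary confounder left out of the model,

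observed HR / true HR = [1 + p1(RR − 1)] / [1 + p0(RR − 1)],

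where p1 and p0 are the prevalences in the matched Tio/Olo and ICS/LABA groups and RR is the risk ratio for pneumonia hospitalisation. All values are assumptions, and the proxies are ignored.

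| p1 vs p0 | ASD | RR 1.5 | RR 2 | RR 3 |
|---|---|---|---|---|
| 5% vs 5% | 0.00 | 1.00 | 1.00 | 1.00 |
| 6% vs 5% | 0.04 | 1.00 | 1.01 | 1.02 |
| 8% vs 5% | 0.12 | 1.01 | 1.03 | 1.05 |
| 10% vs 5% | 0.19 | 1.02 | 1.05 | 1.09 |
| 2% vs 4% | 0.12 | 0.99 | 0.98 | 0.96 |
| 3% vs 6% | 0.15 | 0.99 | 0.97 | 0.95 |
| 5% vs 10% | 0.19 | 0.98 | 0.95 | 0.92 |

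Extremes: (1 + 0.10×2)/(1 + 0.05×2) = 1.20/1.10 = 1.09, and 1.10/1.20 = 0.92. An assumed true HR of 0.80 would read between 0.80 × 0.917 = 0.73 and 0.80 × 1.091 = 0.87.

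**5. What would a Table 1 row buy?** Every scenario with a factor beyond about 2% either way has an ASD above 0.1, so the SAP's own rule would trigger adjustment. At p0 = 5%, an ASD of 0.1 corresponds to p1 of about 7.4%: 0.024/√[(0.074×0.926 + 0.05×0.95)/2] = 0.024/0.241 = 0.10. The largest factor that could then go unadjusted, at RR 3, is 1.148/1.10 = 1.04.

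**The case against.** The SAP has a fair defence, and much of it stands.

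- **Two variables should not be merged.** A reader might infer that the protocol defines baseline pneumonia as any recorded diagnosis and that Appendix 4 contradicts it. The protocol line belongs to the severity scale. The comorbidity has no protocol definition, and the propensity-score covariates are delegated to the SAP. Only the severity line conflicts.
- **The absence of a row does not show imbalance.** A reader might infer that outpatient pneumonia is left unbalanced. The documents show only that it is not matched on directly and not checked. The proxies will remove some imbalance, and how much is unknown.
- **The direction is open.** A reader might infer that the gap hides a pneumonia harm of ICS/LABA, because patients with recent pneumonia are steered to Tio/Olo. The protocol's rationale also says guidelines point ICS/LABA at frequent exacerbators and that ICS is widely used inappropriately, so channelling the other way is equally plausible.
- **Inpatient-only is a defensible choice.** Pneumonia is acute and an inpatient code is more specific. The outcome is itself hospitalised pneumonia, and prior inpatient pneumonia is in the score. The Appendix 4 outpatient rule would not capture a single clinic episode either, because it asks for more than two diagnoses.
- **Scope is limited.** The outcome is secondary, and the protocol does not flag it as a safety issue, although the study aim includes the safety profile. Parts of the SAP are redacted, so further analyses cannot be ruled out.

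What survives is the unexplained difference in the severity criterion and the missing balance check. Delegating the choice of covariates does not obviously extend to altering a severity scale that the protocol spells out.

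**Conclusion.** The concern holds in a limited form. The SAP narrows the protocol's severity criterion without a visible reason. With an inpatient-only comorbidity as well, no propensity-score variable or Table 1 row directly records outpatient pneumonia, and the ASD rule cannot reach it.

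The documents do not allow the effect on the pneumonia HR to be derived. Under the assumed prevalences and RR of 1.5 to 3 it is about 0 to 9% in either direction, including no effect if the groups are balanced. The upper end supposes an ASD near 0.19 persisting after matching on the proxies, so the realistic figure is likely smaller. This is an inexpensive improvement to a secondary comparison and a consistency correction to a covariate used throughout. It is not evidence that the pneumonia result will be biased.

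**What to change.** 1. Reconcile the pneumonia criterion for Severe COPD between Protocol 9.3.3 and SAP 7.3. Either use one wording in both, or state in the SAP why the narrower one was chosen.
2. Add a covariate, outpatient pneumonia diagnosis in the 12 months before index (yes/no), using the Appendix 4 pneumonia codes. State whether emergency-room visits count.
3. Enter it in the propensity score and give it a Table 1 row before and after matching, so that the existing ASD rule applies.

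**Cost.** SAP wording and one more binary variable, which should be obtainable from the claims data already in use. Outpatient pneumonia codes are less specific than inpatient ones, so the covariate will carry some misclassification. There may be a few fewer matched pairs.

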## **8. DATA SOURCES**

Data sources include Taiwan National Health Insurance (NHI), Taiwan Cancer Registry (TCR) and Taiwan Mortality Data. Taiwan Department of Statistics, Ministry of Health and Welfare is the unit designated by the government to manage health and social welfare statistical databases, and to develop data platform for academic research. Through the services provided by the Health and Welfare Data Science Center (HWDSC) of the Department of Statistics, researchers may access a wide range of health and welfare data, including claims, mortality (with cause of death) and Taiwan Cancer Registry (TCR). The HWDSC staff encrypt the national ID for all individuals according to a secure encryption

algorithm that is not made known to the public. The encrypted ID is unique for all individuals and will be used for linkage between databases.

## **9. DATA MANAGEMENT AND SOFTWARE/TOOLS**

### **9.1 SOFTWARE/TOOLS**

All analysis will be conducted by Taiwanese collaborators using SAS software version 9.4 (SAS Institute, Inc., Cary, NC).

### **9.2 HANDLING OF MISSING VALUES**

As administrative data routinely submitted to the health authority, there are no missing value in the health insurance claims. Handling of apparently inconsistent is described under section [9.3](#). The small number of subjects with missing information on date of birth or gender will be excluded from the study and described in [Figure 1](#).

### **9.3 HANDLING OF INCONSISTENCIES IN DATA AND OUTLIERS**

No clinical parameter values (such as blood pressure or laboratory examination results) are available, therefore potential outliers of continuous variables are not a major concern.

Apparently inconsistent data, such birth year of 1860 or Tio+Olo prescriptions during the years that it was not covered, would be identified and subjects with inconsistent data will be excluded from analysis and described in [Figure 1](#).

## **10. DATA ANALYSIS**

### **10.1 MAIN ANALYSIS**

All variables, including patient characteristics, baseline measures, and outcomes, will be analyzed descriptively.

- For all analyses, variables will be reported as follows: Continuous variables (e.g., age) will be presented as means (with standard deviation, SD) and/or medians (with interquartile range, IQR), minimum, maximum.

- Categorical variables (e.g., sex) will be presented as absolute and relative frequencies.

All analyses will be presented for each treatment group (Tio+Olo vs LABA/ICS) overall. We will first describe formation of the study cohort. Propensity score (PS) matching will be used to generate two comparable treatment groups. All covariates, except season of index date, will be used to estimate the propensity score with logistic regression. Patients in LABA/ICS group will be individually matched to patients in the Tio/Olo group with 1:1 ratio. A caliper of 0.06 standard deviation of logit (propensity score) will be used to define the range of estimated PS within which to select the comparator. Within that range the LABA/ICS patient with the closest estimated propensity score to the Tio/Olo patient will be selected.

Patient characteristics at baseline in patients treated with Tio+Olo and patients treated with LABA/ICS will be described separately using standard descriptive statistics after propensity score matching. Absolute standardized differences (ASDs) will be used to compare the characteristics between the two groups after propensity score matching, in which a  $>0.1$  ASD indicates a meaningful difference.

All the analyses for primary outcome and secondary outcomes will be performed on patients after propensity score matching. Baseline characteristic table shell are provided in [Table 1](#). The propensity score matching will be carried out once without re-matching.

For the analysis of the primary outcome, individuals will be followed up from the index date until the first moderate or severe COPD exacerbation. The data after the earliest date of the following event would be censored:

- 1) disenrollment
- 2) the end of the study period
- 3) death
- 4) discontinuation of index drug use (a lapse of 45 days without subsequent prescription)
- 5) switching from Tio/Olo to ICS/LABA or from ICS/LABA to Tio/Olo
- 6) escalation to triple therapies (ICS/LAMA/LABA free or fix dose combination)

Note that per study protocol, switching from one ICS/LABA to another ICS/LABA is not a censoring event.

Univariate proportional hazard regression model will be used to compare the time to event between the two treatment groups. It will provide an estimate of the hazard ratio (HR) of time to the first moderate or severe COPD exacerbation associated with Tio+Olo use relative to LABA/ICS use, along with 95% CI. In the event that there are baseline covariates with unequal distribution between the treatment groups, defined as absolute standardized difference larger than 0.1, the covariate(s) will be included in a multiple regression model in addition to the exposure status (Tio/Olo or LABA/ICS).

The analysis of the secondary objectives related to time to triple therapy escalation and time to first hospitalization for community-acquired pneumonia will be univariate proportional hazard regression model with an as-treated approach, similar to that of the primary analysis. The estimate of hazard ratio (HR) of time to triple therapy escalation and first hospitalization for community-acquired pneumonia associated with Tio+Olo use relative to LABA/ICS use,

[figure not shown]
Proprietary confidential information © 2022 Boehringer Ingelheim International GmbH or one or more of its affiliated companies

along with 95% CI will be provided. For the analysis of these time-to-event outcomes, patients will be followed until the event of interest or earliest of the date of the follows, whichever happened first:

- 1) outcome event of interest;
- 2) disenrollment;
- 3) the end of the study period;
- 4) death;
- 5) discontinuation of index drug use (a lapse of 45 days without subsequent prescription)
- 6) switching from Tio/Olo to ICS/LABA or from ICS/LABA to Tio/Olo

In the event that there are baseline covariates with unequal distribution between the treatment groups, defined as absolute standardized difference larger than 0.1, the covariate(s) will be included in a multiple regression model in addition to the exposure status (Tio/Olo or LABA/ICS).

[figure not shown]
Proprietary confidential information © 2022 Boehringer Ingelheim International GmbH or one or more of its affiliated companies

The analysis of the secondary objectives related to annualized rate of prescriptions of rescue medications, the rate ratio of Tio+Olo – exposed group relative to LABA/ICS group, along with 95% CIs will be derived using univariate negative binomial model. Individuals in the study cohort will be followed from the index date until the earliest of the date of:

- 1) disenrollment;
- 2) the end of the study period;
- 3) death;
- 4) discontinuation of the index drug use (a lapse of 45 days without subsequent prescription);
- 5) switching from Tio/Olo to ICS/LABA or from ICS/LABA to Tio/Olo

In the event that there are baseline covariates with unequal distribution between the treatment groups, defined as absolute standardized difference larger than 0.1, the covariate(s) will be included in a multiple regression model in addition to the exposure status (Tio/Olo or LABA/ICS).

For incidence rates, it will be calculated for each cohort as follows:

Incidence rate among the Tio+Olo cohort = (total number of patients in the Tio+Olo cohort experiencing an event of interest for the first time during the given time period) / (total person-time at risk from current use of Tio+Olo during the given period)

Incidence rate among the comparison cohort = (total number of patients in the comparator LABA/ICS cohort experiencing an event of interest for the first time during the given time period) / (total person-time at risk from current use of comparator LABA/ICS during the given period)

The incidence rate ratio (IRR) and incidence difference for the outcome in the Tio+Olo - exposed group relative to that in the comparator group will be derived as follows:

Incidence rate ratio = incidence rate from the Tio+Olo cohort divided by the incidence rate from the matched comparator cohort.

Incidence difference = incidence rate from the Tio+Olo cohort – incidence rate from the matched comparator cohort

For annualized rates, it will be calculated for each cohort as follows:

Annualized rate among the Tio+Olo cohort = (total number of events in the Tio+Olo cohort during the given time period) / (total person-year at risk from current use of Tio+Olo during the given period)

Annualized rate among the comparison cohort = (total number of events in the comparator LABA/ICS cohort during the given time period) / (total person-year at risk from current use of comparator LABA/ICS during the given period)

The incidence rate ratio (IRR) for the triple therapy initiation in the Tio+Olo - exposed group relative to that in the comparator group, along with 95% CIs will be derived using univariate negative binomial model. In the event that there are baseline covariates with unequal distribution between the treatment groups, defined as absolute standardized difference larger than 0.1, the covariate(s) will be included in a multiple regression model in addition to the exposure status (Tio/Olo or LABA/ICS).

For annualized rate of moderate or severe COPD exacerbations and annualized rate of prescriptions of rescue medications, the ratio of Tio+Olo – exposed group relative to LABA/ICS group, along with 95% CIs will be derived using negative binomial model. In the event that there are baseline covariates with unequal distribution between the treatment groups, defined as absolute standardized difference larger than 0.1, the covariate(s) will be included in a multiple regression model in addition to the exposure status (Tio/Olo or LABA/ICS).

SAS codes for negative binomial model are provided in Annex.

